### Protocol for a non-Investigational Medicinal Product (IMP)

This guide is to help researchers with the design and content of protocols for randomised trials that do not involve Investigational Medicinal Product (IMP). It provides advice on the important information that should generally be included in a protocol including some of the methodological considerations specified within Good Clinical Practice (GCP). Further advice can be obtained from the Research Directorate.

#### Protocol Details: V2 18.07.22

#### List of abbreviations and definitions:

**US Ultrasound**

**TLUS Trans-Laryngeal Ultrasound**

**ILO Inducible Laryngeal Obstruction**

**SLT Speech & Language Therapist**

**LTHTR: Lancashire Teaching Hospitals NHS Trust**

**RPH: Royal Preston Hospital**

## Background:

This two-stage study is a pilot to inform further investigations of the feasibility of using ultrasound to view the vocal cords (trans laryngeal ultrasound or TLUS) as a method of looking at vocal cord movements on breathing in. Stage one will look at a population of healthy volunteers. Stage two will look at a cross-section of patients referred to our airways service for assessment of breathlessness.

When healthy, the vocal cords open during breathing in to maximise ventilation. If the vocal cords narrow when breathing in, this can lead to breathing difficulties, and is known as Inducible Laryngeal Obstruction, or ILO. ILO refers to the inappropriate adduction of the vocal folds and or supraglottic structures (above the vocal cords) on inspiration (Christensen et al). ILO is currently coded as ICD 10 Code J38.7 - other disease of larynx.

ILO presents with asthma-like symptoms and is recognised as a “treatable trait” of asthma (ERS, 2020). ILO can make management of acute and chronic “brittle” asthma more challenging, as it is often treated inappropriately medically with high medication burden and high healthcare utilisation, including unnecessary intubation (Newman et al, 1995; Haines et al, 2020; Murphy et al, 2020).

Patients referred for assessment for refractory breathlessness to our Tertiary referral service routinely undergo a diagnostic video laryngoscopy to assess for ILO. This is the current gold standard for assessment and confirmation of diagnosis of ILO. However, accessibility to laryngoscopy for the diagnosis of ILO is limited outside of a specialist centre, and out of hours, even within specialist severe asthma & airways units. Additionally, laryngoscopy is an invasive procedure, and some people cannot tolerate it. Therefore, there is interest to look at supporting investigation into the potential use of less invasive methods of assessing vocal cord movement on breathing in.

Currently, Ultrasound (US) is not widely used as part of the speech and language therapy (SLT) clinical toolkit. Ultrasound assessment of laryngeal function has been described extensively within the literature (Noel et al. 2020) and reported to be a viable method to assess vocal fold function in a population of patients after thyroidectomy (Da Costa et al. 2019).

The COVID-19 pandemic has restricted access and provision of standard SLT procedures including laryngoscopy, due to the risk of increased aerosol generation and disease transmission (Tran et al. 2012, Bolton et al. 2020, RCSLT 2020). Timely access to invasive diagnostic procedures, such as laryngoscopy has therefore been reduced from both staffing capacity and due to infection control and risk of transmission in COVID-19 positive patients.

Ultrasound is a potential addition to SLT instrumental tools as it is a non-invasive, non-ionising and non-aerosol-generating procedure that could be delivered at the bedside in a timely manner to assess laryngeal function. The use of ultrasound to identify patients who may have vocal cord movement impairments, such as vocal fold palsy and paresis has been shown to have high sensitivity and specificity in a recent systematic review and meta-analysis (Allen, Clunie & Slinger, et al 2020).

*The importance of recognising if a patient has ILO:*

The true prevalence of ILO is thought to be underestimated, with the European Respiratory Society and European Laryngological Society reporting that between 24% and 53% of patients with severe asthma have ILO. The prevalence of ILO in all asthma is estimated as 10% of the population.

Currently, there are approximately 5.4 million people in the UK receiving treatment for asthma. Therefore, potentially over half a million people in the UK may have ILO, the majority of whom may be undiagnosed.

Severe asthma affects 5 to 10% of the asthma population but consumes a disproportionate amount of the global asthma budget (~50%) due to unscheduled health care utilisation in primary care, hospitalisations due to severe exacerbations, and the costs of pharmacotherapy, some of which may not be necessary.

A recent systematic review (Lee et al 2020) highlighted ILO as a comorbidity in quarter to a half of asthma cases. In two prospective studies of difficult-to-treat asthma where ILO was suspected, up to 50% of patients were identified as suffering both ILO and asthma. (Low et al 2011, Forrest et al 2012).

A study from the Asthma UK Centre in Applied Research has found that asthma costs the UK health service at least £1.1 billion each year. A UK-wide study, by the Asthma UK Centre for Applied Research, found that there were around 6.4 million GP and nurse consultations for asthma each year. Around 100,000 people are admitted to hospital each year because of asthma attacks.

Of the £1.1b cost of treating asthma in the UK, at least £666 million is spent on prescription costs each year. Other costs include £160m on GP consultations, £143m on disability claims and £137m on hospital care.

In a systematic review and meta-analysis (Murphy et al 2021), patients with comorbid Asthma and ILO accessed healthcare services 39% more than those with Asthma only (n=177/3 studies). ILO intervention by SLT reduced the number of times patients accessed health services by 50.5% (n=275/3 studies) and enabled 74% of patients to reduce or stop Asthma medication (n=191/4 studies).

**A statement of the current service / practice and the relevance of this study to current or new practice:**

Therefore, the potential for early diagnostic screening with TLUS may help identify patients with asthma who also have ILO as treatable trait. If this can be identified, this may help to reduce both healthcare utilisation, allowing health resources to be used more appropriately, and have potential significant impact on morbidity for patients and their families, with potential for significant patient benefit.

Additionally, the prevalence of ILO is thought to be greater in the paediatric population. Therefore, if this study were to prove utility of TLUS in an adult population, there would be potential to evaluate its use in a paediatric population, to prevent any unnecessary treatment escalation and morbidity, as well as offering a less-invasive procedure with potential to be well-tolerated.

## **Aims & Objectives:**

This two-stage pilot study aims to evaluate whether trans laryngeal ultrasound (TLUS) can be a useful tool in the assessment of the abnormal vocal fold movements on inspiration seen in ILO.

The purpose of the two stages of this study is to assess if the use of TLUS is a useful triage screening tool in the assessment of ILO when compared to the current gold-standard reference test of video-laryngoscopy.

Stage one will be conducted with healthy NHS volunteers from the host organisation, (Lancashire Teaching Hospitals NHS Trust) and will look at the degree of success at visualising both vocal cords (right and left), at baseline, during breathing, and when mimicking ILO. The experience of undergoing ultrasound assessment will be looked at via a post-ultrasound scan questionnaire.

Stage two will be conducted with a group of up to 30 patients referred to the Tertiary airways service for breathlessness. We will assess vocal cord movements with simultaneous laryngoscopy (usual care) and TLUS, to investigate whether TLUS has utility as a screening tool to assess the vocal fold movement abnormalities seen in ILO.

### **Primary aims:**

To perform analysis of the range of vocal fold movements on inspiration, using TLUS in healthy volunteers and patients referred to a tertiary airways service.

To assess the sensitivity, specificity and positive predictive value of the use of ultrasound in the assessment of ILO, using Laryngoscopy as reference standard.

To investigate the patient and healthy volunteer perspectives of TLUS assessment of the vocal cords.

### **Secondary aims**

To provide recommendations to inform the development of SLT-led US protocols and make suggestions for further research for its use in assessment of ILO.

To gather information to inform such a protocol, such as impact of age, gender, frequency of probe and approach used to assess vocal fold movement (lateral longitudinal, anterior, thyrohyoid, or crico-thyroid membrane).

To inform the use of static and dynamic assessment techniques using TLUS.

To begin to collect data on variation of vocal fold adduction on inspiration in healthy adults.

To understand how to begin to collect information on measurements of the glottis on inspiration in healthy adults and patients who have confirmed ILO on laryngoscopy.

To collect data on measurements of vocal fold closure associated with a positive diagnosis of ILO.

## **Interventions**

There are no known risks to the patient in the use of laryngeal Ultrasound. The treatment is non-invasive and does not involve radioactive substances.

As the patient will be undergoing usual care, there is no risk of missing an ILO diagnosis.

The treatments will be performed by the PI (CS) and laryngoscopy by the SLT involved in the patient's usual care. After assessment and diagnosis, patients will continue along their usual care pathway, i.e., if ILO is confirmed they will be offered SLT intervention for ILO, and if ILO is not confirmed will continue along the Asthma pathway for medical management.

## **Proposed methods:**

### **Stage one: healthy controls:**

Volunteers will be recruited from NHS staff at the host organisation (LTHTR). Healthy volunteers will be given an information leaflet and consent form upon providing an expression of interest.

Informed consent will be taken by the PI from healthy volunteers who decide to go ahead. It will be stressed that participation and consent can be withdrawn at any time. The consent process itself will take place before the procedure and will be taken by the PI (CS). Consent will be taken in a separate and private room (either the booking-in room in the endoscopy department at RPH, or a separate clinic room in the chest Clinic). This will be completed before the procedure and before entry into the room where the ultrasound procedure will take place.

The consent forms will be stored in a locked cabinet in PI's office. Longer-term, study documents including data and investigator site files will be archived at the Trust's off site archiving facility following local procedures.

Healthy volunteers will be allocated a time and date to attend Chest clinic, or the Endoscopy department at the host organisation, Royal Preston Hospital (RPH) for the scanning session. The scan will be carried out in a private room using transmission gel. Access only to the neck area is required, with privacy and dignity always respected.

The PI will perform an US scan of the larynx, using the Vscan Air (GE), using a protocol designed by the PI. The scan is recorded and stored securely using GE's system. A proportion of scan will be sent to the study collaborator ([name]) and a Specialist Head & Neck Sonographer securely and anonymously with no patient identifiable information included in order to confirm findings when there is uncertainty, and in order to ensure inter-rater reliability.

The scan will consist of a "sweep" of the larynx to identify the main landmarks (hyoid bone, thyroid cartilage, arytenoid cartilages, vocal cords and false vocal cords). A recording form has been prepared for ease of recording. An anonymised code number will be assigned to the Healthy volunteer.

A record will be taken of the frequency in MHz and depth that successful visualisation of the vocal cords occurred to help inform future studies and refine the protocol. Any other factors that are deemed useful to include to help replicate findings and improve image quality and scanning success will also be recorded (such as gain used, high or low, and approach transverse, or lateral longitudinal, and the use of any pre-sets such as Neo-head, lung or small parts).

When the vocal cords are visualised, the healthy volunteer will be asked to breathe normally, take 3 deep inspirations, and then, say “ee” for a sustained period. They will then be asked to breath hold, then take a deep breath in (3 trials), and then mimic ILO (the PI will discuss how to do this before the scan takes place). The commands for each of the above will be in the same order for each patient, as there is no accompanying sound, this will allow for easier analysis to be able to differentiate each vocal cord movement according to what the volunteer was asked to do.

Following the procedure, the volunteer will be given an electronic questionnaire to complete, so that feedback on their experience can be gained and used as part of writing up of findings.

[https://forms.office.com/pages/designpagev2.aspx?lang=en-US&origin=OfficeDotCom&route=Start&subpage=design&id=gmOokJ\\_8nEW5GphS-wiyzcd-VqpQSdVGguxTgVT2MfRUMEZUNUoxT1YyQkIPOEVVM0VQVVpJRUVEUS4u](https://forms.office.com/pages/designpagev2.aspx?lang=en-US&origin=OfficeDotCom&route=Start&subpage=design&id=gmOokJ_8nEW5GphS-wiyzcd-VqpQSdVGguxTgVT2MfRUMEZUNUoxT1YyQkIPOEVVM0VQVVpJRUVEUS4u)

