### **Stage two: patient population**

A sample of 30 participants will be recruited from consecutive patients referred to our NHS Tertiary Airways service for assessment for complex breathlessness and ILO. Participants will be asked at initial assessment, after they have consented to the laryngoscopy, if they would wish to undergo TLUS concurrently with their usual care of diagnostic laryngoscopy.

An information leaflet will be given, and written consent form completed with the patient by the PI. Written Information will be provided at the point of initial consultation (at least 48 hours before the planned procedure. Written consent will take place at the appointment for the Laryngoscopy (usual care for laryngoscopy), by the PI (CS). A witness will not be present. Consent will take place in a private booking-in room that is part of usual care for patients attending for laryngoscopy assessment for ILO). Patients have more than 48 hours to consider the information and decide if they would like to participate.

Patients who require an interpreter for their initial consultation will be provided with information via the interpreter of the study.

Patients will be informed that usual care will not be affected by their decision to participate or not, and that consent can be withdrawn at any point. If the patient finds dual assessment with laryngoscopy and TLUS too invasive or distressing, they can withdraw consent, and the TLUS will be stopped.

It is envisaged that the TLUS operator (PI) will perform the US assessment whilst another SLT completes the laryngoscopy (usual care) and works through the usual diagnostic laryngoscopy provocation protocol to induce symptoms. The US-operating SLT will take a note of settings to achieve image acquisition and will take note of vocal fold movements on an anonymised recording form with subject allocation number identified.

The SLT operators (TLUS and laryngoscopy) will be blinded to the images and results of the other assessment (either TLUS or laryngoscopy), as the screen for the Laryngoscopy system can be rotated away to be unobservable by the US-operator SLT. Following the procedure, the SLT conducting the US will leave the endoscopy theatre room to allow for usual debrief to occur with the patient (usual care). After this, the patient will be asked to complete a short questionnaire electronically to elicit their experience of TLUS.

<https://forms.office.com/pages/designpagev2.aspx?lang=en->

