Following the clinical session, the results of the TLUS and laryngoscopy will be compared for outcome and record made (on the reporting form) of the assessments compared, and any false positive or negative results will be documented, along with ability to visualise either or both vocal folds (left and right).

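### Settings are recorded where the vocal cords were seen, with no log of unsuccessful attempts, so the effect of probe frequency and depth on visualisation cannot be estimated

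*Combined protocol and SAP*

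**What the plan says.** The Secondary aims include gathering information for a future SLT-led ultrasound protocol, with examples given as "impact of age, gender, frequency of probe and approach used to assess vocal fold movement".

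Three statements govern what is recorded about settings:

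- Stage one, frequency and depth: "A record will be taken of the frequency in MHz and depth that successful visualisation of the vocal cords occurred".
- Stage one, everything else: "Any other factors that are deemed useful to include to help replicate findings and improve image quality and scanning success will also be recorded". The examples in that sentence are gain, pre-sets and "approach transverse, or lateral longitudinal".
- Stage two: "The US-operating SLT will take a note of settings to achieve image acquisition".

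Whether the folds were seen at all is captured separately. Under Aims & Objectives, stage one "will look at the degree of success at visualising both vocal cords (right and left), at baseline, during breathing, and when mimicking ILO". In stage two, the comparison record made after the session covers false results "along with ability to visualise either or both vocal folds (left and right".

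Data analysis plans confidence intervals for visualisation, but no breakdown by frequency, depth, approach, age or sex. Study end definition allows early closure if few views succeed in stage one, which presupposes that unsuccessful views are counted.

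**The concern.** Asking what impact a setting has means asking how often it works when it is tried. That needs the failures at the setting as well as the successes. The stage one rule for frequency and depth is conditioned on success. The stage two wording is less explicit but most naturally means the settings that produced an image. A participant whose folds are seen on the third attempt becomes one success at the third setting, and the two failed attempts leave no trace.

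A list of successful settings then partly reflects habit. Whatever the operator tries first on everyone will dominate the list even if it often fails. Recommendations for an SLT-led protocol are themselves a secondary aim, so this weakness falls on one of the pilot's intended outputs. Unlogged attempts may not be recoverable later, so the point is best settled before scanning starts.

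**Working it through.** The documents give no figure on this point to reproduce. The check is a reading of the capture rules, followed by illustrations on assumed counts.

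**1. What can be linked to what**

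| Quantity | Successes known? | Failures known? |
|---|---|---|
| Overall visualisation, per participant | Yes | Yes (Aims & Objectives; Stage two; Study end definition) |
| By age or sex, per participant | Yes, if age and sex are noted | Yes, on the same condition |
| By frequency or depth | Yes | Not required in either stage |
| By approach, gain or pre-set | At discretion | Not required; depends on the unseen form |

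**2. What missing failures do to a comparison (assumed counts)**

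Suppose 30 people are scanned, one setting is attributed to each, and 24 are visualised: 16 at setting A and 8 at setting B. The other 6 are failures with no setting recorded. Let f of the 6 belong to A.

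- Success at A = 16 / (16 + f)
- Success at B = 8 / (8 + 6 - f)

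| f | A | B | A minus B (points) |
|---|---|---|---|
| 0 | 100% | 57.1% | +42.9 |
| 2 | 88.9% | 66.7% | +22.2 |
| 4 | 80.0% | 80.0% | 0.0 |
| 6 | 72.7% | 100% | -27.3 |

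Overall success, 24/30 = 80%, is known throughout. The direction of the difference between settings is not. If several settings are tried per person, the number of failed attempts is also unknown and the range widens.

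**3. Why a share of successes is not a success rate (assumed counts)**

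Suppose A is tried first in 30 people and works in 15 (15/30 = 50%). B is then tried in 10 of A's failures and works in 9 (9/10 = 90%). The success list shows A in 15/24 = 62.5% and B in 9/24 = 37.5%. The list follows order of use. The 50% and 90% do not rank the settings either, because B was tried only in people in whom A had failed.

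**4. What complete logging could support (assumed rates)**

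Take two independent groups of 15 (30 split equally), two-sided alpha 0.05, with p̄ the mean of p1 and p2 and d = p1 - p2:

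- Power = Φ{ [ |d|√n - 1.96√(2p̄(1-p̄)) ] / √(p1(1-p1) + p2(1-p2)) }
- n per group for 80% power = [ 1.96√(2p̄(1-p̄)) + 0.842√(p1(1-p1) + p2(1-p2)) ]² / d²

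| p1 v p2 | Power at 15 v 15 | n per group for 80% power |
|---|---|---|
| 90% v 70% | 27% | 62 |
| 80% v 60% | 22% | 82 |
| 90% v 50% | 68% | 20 |

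For 90% v 70%: (0.2 × 3.873 - 1.96 × 0.566) / 0.548 = -0.61, and Φ(-0.61) = 27%. Even a full log supports description, not a test between settings.

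**The case against.** The best defence is that this is a pilot, and the aim is to gather information, not to test a hypothesis. A description of frequencies, depths and approaches that worked serves part of that aim. A recording form has been prepared, scanning follows a protocol written by the investigator, and stage one scans are stored. None of these is shown in detail, so unsuccessful attempts may in fact be captured. Settings are chosen by the operator and tried in sequence, so even a complete log would not isolate the effect of one setting. A scan described as a sweep may not divide neatly into attempts.

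Much of this stands. It rules out three stronger conclusions that a reader might draw:

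- *That approach is also recorded only on success.* The success condition is attached to frequency and depth. Approach sits in a separate sentence, which is discretionary but not limited to successful views.
- *That failures have no denominator at all.* They are counted per participant in both stages. Only the link to a setting is missing, so the age and gender parts of the aim are not blocked.
- *That the data will not exist, or that the aim cannot be met.* The text supports not required, which is weaker than not collected, and a list of workable settings is still possible.

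What the defence does not answer is that no section requires an unsuccessful frequency, depth or approach to be logged with its outcome. Discretionary notes and stored images do not guarantee that it will be.

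**Conclusion.** The point holds in a limited form. Followed as written, the plan yields overall visualisation success and can yield success by age and sex, assuming both are noted for each participant. It cannot yield success rates by frequency or depth. The same is true of approach unless the unseen form records failed attempts. What remains is a list of settings that worked, which may reflect the operator's first choice.

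In the assumed example the resulting uncertainty runs from -27 to +43 percentage points, so even the sign of the difference is undetermined. That range depends on the assumed counts. The underlying point, that a rate needs failures at the same setting, does not.

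One exploratory secondary aim is affected. The primary aims on movement, diagnostic accuracy and participant experience do not depend on it. The change is worth making because it is cheap and easiest before data collection.

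**What to change.** **Recording form, both stages.** List each approach and each frequency, depth and pre-set combination attempted, in order, with right fold seen (yes/no) and left fold seen (yes/no). Record age and sex. Define an attempt, for example as any change of approach or of one of those settings, so that a sweep can be coded consistently.

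**Approach categories.** Use one set throughout. The Secondary aims name lateral longitudinal, anterior, thyrohyoid and crico-thyroid membrane; Stage one names transverse and lateral longitudinal.

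**Data analysis.** Add one descriptive table:

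- successes over attempts by approach and by frequency, with exact 95% confidence intervals, counting each participant once per category so that the binomial interval applies;
- first-attempt success shown separately, because later attempts follow failures;
- participant-level success by age and sex.

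State that the table is descriptive and does not isolate the effect of a setting, since settings are operator-chosen, tried in sequence and seen in few people. No hypothesis test is needed.

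**Cost.** A few extra boxes per scan and one table. The downside is slightly longer form-filling during the scan. If the existing form already captures every attempt, the protocol need only say so and add the table.

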**Data collection and handling:**

Written recording forms will be marked with an anonymous participant code. Data from recording forms for stage one and stage two will be extracted and inputted into the SPSS statistical analysis package by the PI. Recording forms will be stored in a locked filing cabinet in the SLT NHS office.

Data from participant questionnaires from stage one and stage two will be downloaded from Microsoft Forms into a Microsoft Excel database. All digital database files will be stored on a password-protected NHS laptop. Long-term arrangements: Study documents including data and investigator site files will be archived at the Trust's off site archiving facility following local procedures.

The Vscan Air ultrasound system allows clinicians to securely share data and images and includes sharing auto-anonymized images with other apps, with no cloud requirement.

Images will be stored on a NHS laptop which is password protected and will be stored in a password-protected file.

All data will be anonymised via a combination of identifier as a healthy volunteer (HV) or patient (PT) and participant number, followed by the date of clinic (e.g HV1 18.07.22, or for patients PT118.07.22).

Data for healthy volunteer and patients will be analysed by the Principal Investigator electronically on an NHS laptop.

Advice will be sought from LTHTR research team regarding support for statistical analysis of data, but all patient identifiable data will be removed before this stage.

Research data will be stored electronically, which will comprise scanned consent forms and questionnaires, US and laryngoscopy images, examination data recording sheets and statistical data. Electronic data will be stored on the NHS Trust server in a password-protected folder, accessed only by the Principal Investigator.

Study documents including data and investigator site files will be archived at the Trust's off site archiving facility following local procedures.

Identifiable personal data for the healthy volunteers or the patient participants will not be used for either stage 1 or 2.

Healthy volunteer consent forms and any data will be kept in a separate file, and no access to medical records will be made for these patients. The local SOP for Research with Health Volunteers will be followed.

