### **Data analysis:**

The outcomes of the TLUS and laryngoscopy assessments in stage one and stage two and will be analysed using SPSS. 2 x 2 tables will be generated to calculate values of sensitivity (whether a participant can be confirmed as having ILO, or mimicked ILO) and specificity (whether ILO, or mimicked ILO, can be ruled out for a participant), and confidence intervals for visualisation of the vocal folds using TLUS. In stage two, percentage agreement between TLUS and laryngoscopy for confirmation or non-confirmation of ILO will also be calculated.

The values, if available, for measurements of the distance between the arytenoids for healthy volunteers and patients during normal breathing, deep inspiration, and during ILO (mimic in stage 1 and actual in stage 2), will be analysed via a non-parametric comparison of means within SPSS.

Quantitative questionnaire data will be analysed using Microsoft Excel to generate mean values and ranges. Qualitative questionnaire data will be analysed using thematic analysis (Braun and Clarke, 2006), with themes generated to aid understanding of participants' experiences of the TLUS and laryngoscopy procedures.

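### Stage one plans sensitivity and specificity for mimicked ILO, but the fixed command order tells the reader which segment is the mimic and no masked read is planned

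*Combined protocol and SAP*

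**What the plan says.** Under Stage one: healthy controls, the volunteer breathes normally, takes deep inspirations, phonates, holds the breath, takes further deep breaths in, and finally mimics ILO. The mimic is coached beforehand: "then mimic ILO (the PI will discuss how to do this before the scan takes place". The order does not vary: "The commands for each of the above will be in the same order for each patient, as there is no accompanying sound". The stated purpose is to make it easier to "differentiate each vocal cord movement according to what the volunteer was asked to do".

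The same section says who scans: "The PI will perform an US scan of the larynx, using the Vscan Air (GE), using a protocol designed by the PI". Data collection and handling adds: "Data for healthy volunteer and patients will be analysed by the Principal Investigator electronically on an NHS laptop". A proportion of scans goes, without patient identifiers, to a collaborator and a specialist sonographer "in order to confirm findings when there is uncertainty, and in order to ensure inter-rater reliability".

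Data analysis covers both stages with 2 x 2 tables and defines "sensitivity (whether a participant can be confirmed as having ILO, or mimicked ILO", with specificity defined in the matching way. Blinding between operators is described only under Stage two: patient population.

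**The concern.** A test accuracy estimate needs an index reading made without knowledge of the reference state. In stage one the reference state can only be the command, and the fixed order puts that command at a known place on the recording. A reader who could not tell the mimic from a breath hold, phonation or a deep inspiration could still label every mimic correctly.

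At stake is the mimicked-ILO sensitivity and specificity from stage one. A high value would look like early evidence that ultrasound can show ILO-type adduction, although the same value could arise with no information from the image.

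**Working it through.** The protocol states no accuracy target, power or stage one sample size, so there is no planned figure to reproduce. The check sets the passages side by side and then scores a reader who never looks at the image.

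**What the passages imply together**

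1. *Reference.* The first sentence of Data analysis mentions laryngoscopy alongside both stages, but the stage one procedure contains none. The command is the only reference available.
2. *Reader.* The PI coaches the mimic, designs and performs the scan, and analyses the data. No one else is described in the session, so it is inferred, not stated, that the PI gives the commands and makes the call.
3. *Second readers.* Their scans are anonymous as to identity. Nothing says they are masked to task or order, and nothing says whether they know the sequence.
4. *Unit.* Data analysis defines both measures per participant, but every volunteer is asked to mimic. With the command as reference there are no negative participants, so specificity is undefined at that level. Only the segment, or clip, can be the unit.

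**A reader who always calls the last segment the mimic**

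Assumption: the sequence is counted as k = 6 segments (normal breathing, deep inspirations, phonation, breath hold, deep breaths in, mimic), with n volunteers.

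- *Fixed order, known to the reader.* Sensitivity = n/n = 100%. Specificity = 5n/5n = 100%.
- *Order hidden, one clip per volunteer called the mimic without using the image.* Sensitivity = 1/k = 1/6 = 16.7%. The one wrong call, made with probability 5/6, falls on one of 5 non-mimic clips, so the false-positive rate is (5/6)/5 = 1/6 and specificity = 5/6 = 83.3%. Youden index = 1/6 + 5/6 − 1 = 0. A simulation of 100,000 volunteers with the mimic's position random and unknown to the reader gave 16.6% and 83.3%.
- *Other segment counts.* Sensitivity is 1/k and specificity (k − 1)/k, so the Youden index is 0 for any k. With two clips, one mimic and one deep inspiration, the figures are 50% and 50%.

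**How convincing the uninformative result could look**

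For n correct out of n, the exact (Clopper-Pearson) 95% lower limit is 0.025^(1/n). Stage one n is not given, so a range is assumed:

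| n (assumed) | Observed sensitivity | 95% lower limit |
|---|---|---|
| 10 | 100% | 69.2% |
| 20 | 100% | 83.2% |
| 30 | 100% | 88.4% |

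These limits reflect sampling error only. They say nothing about whether the image or the position produced the score.

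**The case against.** The best defence is that the fixed order has a sound purpose. The recordings are silent, and order is a simple way to label each task. Keeping the mimic last also stops a coached abnormal manoeuvre from preceding the normal-breathing and inspiration recordings, which serve the aims of describing movement in healthy adults. This stands: the defect is the unmasked read, not the order. Varying the order would not mask someone who coaches and commands in any case.

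A second defence is that stage one is mainly about visualisation. Aims & Objectives describes it as success at seeing both cords, including during the mimic, plus participant experience. The closure criterion under Study end definition turns on limited successful views, not on recognising the mimic. This also stands, and it limits the scope of the point. It does not remove it, because Data analysis still puts mimicked ILO into the accuracy tables.

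A third defence is the second reading. It is a partial safeguard at most. It covers an unstated proportion of scans, chosen partly because the finding was uncertain, and no masking to task or order is described. It would be too strong to say that those readers do know the order; the documents leave that open.

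A reader might also infer that measured distances during the mimic are distorted by the tasks before it. No passage supports such a carry-over effect, and the point does not rely on one.

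**Conclusion.** The point holds for one planned result, the stage one sensitivity and specificity for mimicked ILO. Followed as written, the plan allows 100% on both measures with no contribution from the image, so the result could not be read as evidence of what ultrasound shows. This rests on the command being the reference, which follows from the stage one procedure, and on the PI giving the commands and reading the scan, which is inferred. The 16.7% and 83.3% comparison also rests on counting six segments; the conclusion of no discrimination does not depend on that count.

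A reader might go further and conclude that stage one tells us nothing about ultrasound. The documents do not support that. Success at visualising the cords, the early-closure rule and stage two accuracy against laryngoscopy are unaffected. Inter-arytenoid distances can still be measured, though whoever measures them would be unmasked to the task.

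**What to change.** Keep the acquisition order and separate the reading from it.

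1. Save each command as its own clip, or log clip times on the recording form. Give the clips neutral codes and shuffle them.
2. For scans already going to the collaborator or sonographer, have that reader classify each clip as mimic or not mimic without knowing task or order.
3. Choose the scans for this read consecutively or at random, and state how many. Scans sent because of uncertainty can still go, but should not feed the estimate.
4. Base any mimicked-ILO sensitivity and specificity on this masked read only, with the clip as the unit. Intervals for specificity should allow for several clips coming from one volunteer.

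The alternative is to delete sensitivity and specificity for mimicked ILO from Data analysis and report stage one as visualisation and measurement only.

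The first option adds clip handling but no scans or staff. Its main cost is precision, because the estimate rests on a subset. For illustration, if 10 of an assumed 30 volunteers were read and all mimics were recognised, the lower limit for sensitivity would be 69.2% instead of 88.4%. The second option costs only the loss of a result that could not be interpreted as planned.
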